KCCQ: Kansas City Cardiomyopathy Questionnaire

mRS: Modified Rankin Scale

NIHSS: National Institute of Health Stroke Scale

QoL: Quality of Life

TAVR: Transcatheter Aortic Valve Replacement

VARC: Valve Academic Research Consortium

PROTOCOL SUMMARY

Title:	WATCHMAN for Patients With Atrial Fibrillation Undergoing Transcatheter Aortic Valve Replacement
Short Title:	WATCHMAN and TAVR
Objectives:	To evaluate the safety and effectiveness of the left atrial appendage occlusion with WATCHMAN Device in prevention of stroke and bleeding in patients with atrial fibrillation (AF) undergoing transcatheter aortic valve replacement (TAVR).
Endpoints	Primary Endpoint: Composite of all-cause mortality, stroke (ischemic and hemorrhagic), and bleeding (life-threatening and major) events. Secondary Endpoints: All-cause mortality, stroke (ischemic and hemorrhagic), bleeding (major and/or life-threatening as per VARC2 definitions), cardiovascular mortality, arterial or venous thrombosis or embolism, rehospitalization

related to WATCHMAN procedure or device, QoL (KCCQ) at follow-up, and procedural costs for both TAVR and WATCHMAN.

Population: The WATCHMAN device is FDA approved for stroke prevention in patients with non-valvular atrial fibrillation defined as “Atrial fibrillation in the absence of rheumatic mitral valvular heart disease”. The current study aims to investigate the outcomes of implantation of the WATCHMAN device in patients with non-valvular AF undergoing FDA approved TAVR.

Phase: IV

Number of Sites enrolling participants: Approximately 33 US sites

Description of Study Agent: The WATCHMAN device is a self-expanding left atrial appendage closure (LAAC) device with a porous covering on the proximal face.

Device sizes: 21 mm, 24 mm, 27 mm, 30 mm, 33 mm

Study Design: WATCH-TAVR is a prospective, multicenter, randomized event-driven controlled trial. Only centers with approval for commercial WATCHMAN implantation will be included in this trial. Subjects will be enrolled at approximately 33 centers in the United States. There will be approximately 350 subjects enrolled, with 175 patients being randomized to TAVR + medical therapy and 175 patients randomized to simultaneous TAVR+WATCHMAN to accumulate the 191 primary events needed. Patients with non-valvular AF undergoing standard of care TAVR will be enrolled in the trial.

Patients randomized to receive the WATCHMAN device will receive anticoagulation with warfarin and aspirin for 6 weeks after the procedure. After 6 weeks, the plan of care will follow WATCHMAN labeling. Patients randomized to the TAVR + medical therapy arm will be treated in accordance with standard of care with either warfarin, other anticoagulant/antiplatelet therapy, or no anticoagulation at the discretion of the treating physician. All patients will continue to receive routine post-TAVR follow-up and care.

Patients will be monitored for primary and secondary endpoints as outlined. Baseline information and laboratory data will be collected as described in the protocol.

Selection Criteria Inclusion Criteria: Determination for participation in the study is based upon standard of care practice for assessment of TAVR & WATCHMAN eligibility.

1. Men and Women \geq 18 years of age

2. The patient meets criteria for and is eligible to undergo TAVR procedure
3. The patient has documented paroxysmal, persistent, or permanent atrial fibrillation
4. The patient meets the WATCHMAN labeling guidelines and is eligible to undergo the WATCHMAN implantation procedure
5. The patient is eligible for short term warfarin therapy
6. The patient or legal representative is able to understand and willing to provide written informed consent to participate in the trial
7. The patient is able and willing to return for required follow-up visits and examinations

Exclusion Criteria:

1. The patient had a stroke or TIA within the last 6 months prior to enrollment
2. Contraindication for short term anticoagulation
3. Moderate or severe MS with mean gradient across MV >10 mm Hg of MVA $< 1.2\text{cm}^2$.
4. The patient has symptomatic carotid disease (i.e., carotid stenosis $\geq 50\%$ associated with ipsilateral transient or visual TIA evidenced by amaurosis fugax, ipsilateral hemispheric TIAs or ipsilateral stroke within 6 months)
5. Prior occlusion of LAA
6. The patient has an implanted mechanical mitral valve
7. The patient *requires* long-term warfarin therapy due to:
 - a. Secondary to conditions such as prior arterial embolism or other indications such as pulmonary embolism or deep vein thrombosis within the previous 6 months
 - b. The patient is in a hypercoagulable state; exclude the patient if per medical record documentation, the patient meets any of the following criteria:
 - Thrombosis occurring at under 40 years age
 - Idiopathic or recurrent VTE (venous thromboembolism)
 - Thrombosis at an unusual site (cerebral veins, hepatic veins, renal veins, IVC, mesenteric veins)
 - Family history of VTE or of inherited prothrombotic disorder, recurrence/extension of thrombosis while adequately anti-coagulated
8. The patient is actively enrolled in another trial of a cardiovascular device or an investigational drug (post-market study participation and registries are acceptable)

9. The patient is pregnant or pregnancy is planned during the course of the investigation if patient is of child bearing potential
10. Any clinically significant medical condition or presence of any laboratory abnormality performed prior to randomization that is considered by the investigator to be clinically important and could interfere with the conduct of the study or not meeting procedure guidelines for TAVR or WATCHMAN
11. The patient has a life expectancy of less than two years

Participant Duration: 2 Years

(This section is intentionally left blank)

1 INTRODUCTION: BACKGROUND INFORMATION AND SCIENTIFIC RATIONALE

1.1 BACKGROUND INFORMATION

Atrial fibrillation (AF) is a common baseline comorbidity and the commonest arrhythmia in patients with aortic stenosis (AS) undergoing Transcatheter Aortic Valve Replacement (TAVR). AF is a known risk factor for stroke during or after TAVR, associated with stroke, bleeding complications, worse outcomes and increased mortality¹. The TAVR population is at increased long-term bleeding risk, with cognitive impairment, high risk of falls, history of spontaneous bleeding, etc. Standard medical therapy for emboli prevention in AF, long term oral anticoagulation (OAC), carries risk of hemorrhagic stroke, as well as major bleeding complications². Anti-platelets prescribed after TAVR, combined with OAC, worsen bleeding risk further³. Left atrial appendage closure is an alternative to OAC, which obviates the need for regular medication and frequent monitoring. The WATCHMAN Left Atrial Appendage Closure (LAAC) System is the only device that has been approved by the FDA for preventing thrombo-embolic events in patients with non-valvular atrial fibrillation (AF)⁴. Non-valvular AF is defined as atrial fibrillation in the absence of rheumatic mitral valvular heart disease⁵. The WATCHMAN device has shown improved safety compared to OAC, with reduced event rates for hemorrhagic stroke and major bleeding in patients receiving the implant^{6,7}. There are only small reports of feasibility of the procedure⁸. Randomized trials with the WATCHMAN device have excluded patients with valvular heart disease. As a result, data on safety and efficacy of the device in TAVR patients with AF is lacking⁹.

1.2 RATIONALE

The WATCH-TAVR study aims to investigate the safety and efficacy of the WATCHMAN device in patients with AF who have severe AS and are undergoing TAVR. In addition, the simultaneous procedure arm aims to combine two device-related procedures into one single procedure, thereby exposing the patient to only one hospitalization and general anesthesia, potentially reducing risks in an already elderly and frail population. The combined procedure also allows a common venous access to be obtained for temporary pacing and delivery of the WATCHMAN device. The combined procedure, OR time, TEE and fluoroscopy may reduce costs to the patient. The trial is feasible and has the potential to have impactful and practice changing results.

1.3 POTENTIAL RISKS AND BENEFITS

1.3.1 KNOWN POTENTIAL RISKS

Potential surgical risks associated with the WATCHMAN implant procedure are similar to those encountered peri- and postoperatively for many routine catheterization procedures.

In addition to the general surgical risks, additional risks specifically associated with the WATCHMAN implant are as follows:

- Additional surgery if the device is not placed in the correct position
- Allergic reaction to the implant materials
- Device misplacement
- Device embolization
- Device fracture or extrusion
- Excessive bleeding
- Hypertrophic scarring or thrombosed veins
- Inability to move or retrieve device

Patients who receive the WATCHMAN implant should stop warfarin therapy at the 45-day follow-up visit; therefore, at that time, patients may be at an increased risk of stroke. Warfarin is the proven standard of care for reducing the risk of stroke in atrial fibrillation.

Risks associated with long term warfarin therapy are:

- Fatal or nonfatal hemorrhage from any tissue or organ
- Bleeding which occurs when PT/INR is within the therapeutic range warrants diagnostic investigation since it may unmask a previously unsuspected lesion, e.g., tumor, ulcer, etc.
- Necrosis of skin and other tissues.
- See ADVERSE REACTIONS section of warfarin tablets package insert.

1.3.2 KNOWN POTENTIAL BENEFITS

The WATCHMAN device has been FDA approved to prevent thrombo-embolic events originating from the LAA. However trials with the WATCHMAN device have excluded any patient with an Aortic Valve Area < 1.0 cm². In patients with AS, the primary site of thrombus origin has been demonstrated to be the LAA. This makes the WATCHMAN device potentially beneficial in stroke prevention for patients with AS. The device also has improved safety compared to oral anticoagulation, with less bleeding and hemorrhagic stroke rates.

The simultaneous TAVR and WATCHMAN procedure will share anesthesia time, OR time, TEE and hospital admission costs. By avoiding two separate general anesthesia events, risks to the patient are reduced. Risks of bleeding associated with two separate intra-procedure heparinization are also avoided.

Long term oral anticoagulation carries with it an elevated risk of bleeding. The general population of patients undergoing TAVR are elderly and have high frailty scores, increasing risks of bleeding further. Device based thrombo-embolism prevention will avoid these increased bleeding risks and possibly improve quality of life. It will also obviate the need for regular medication, decrease drug-drug interactions in a population already on multiple medications, and reduce the need for regular monitoring of INR levels.

2 OBJECTIVES AND PURPOSE

The WATCH-TAVR study is designed to evaluate the safety and effectiveness of left atrial appendage occlusion with the WATCHMAN device in the prevention of stroke and bleeding in patients with atrial fibrillation undergoing transcatheter aortic valve replacement (TAVR).

The efficacy of the WATCHMAN device has been previously demonstrated in patients with non-valvular AF who are eligible for warfarin therapy. Until now, trials with the WATCHMAN device have excluded patients with aortic stenosis (AVA <1.0cm²). There is no conclusive evidence of the benefit of the device in patients with severe AS. A large portion of patients with severe AS who undergo TAVR are known to have AF. This increases stroke risk dramatically after the procedure and is associated with worse outcomes. Standard medical therapy, i.e. anticoagulation is associated with increased risks of bleeding, including major bleeds and intra-cranial hemorrhage. There is a lack of clear consensus guidelines regarding the use of anticoagulation in AF after TAVR. In addition, many patients are unsuitable candidates for long term anticoagulation and need an alternative approach to stroke prevention. This study aims to establish the efficacy and safety of the WATCHMAN device in preventing stroke and bleeding in patients with AF undergoing TAVR.

3 STUDY DESIGN AND ENDPOINTS

3.1 DESCRIPTION OF THE STUDY DESIGN

The WATCH-TAVR study is a prospective, multicenter, randomized trial to be conducted at approximately 33 centers in the U.S. The trial aims to enroll approximately 350 patients to accumulate the necessary 191 primary events. Enrollment is expected to occur over the course of 18 months. Patients will be followed up for a total of 2 years.

Eligible patients from each investigator's patient population shall be screened as potential candidates for the WATCH-TAVR study. The patient's history and baseline clinical parameters will be reviewed and written informed consent to participate will be obtained. The fulfillment of all inclusion and exclusion criteria shall be assessed and further baseline parameters necessary prior to randomization shall be obtained. Patients will be randomized to TAVR procedure alone or TAVR procedure combined with the WATCHMAN procedure. Determination for participation in the study is based upon standard of care practice for assessment of TAVR & WATCHMAN eligibility.

It is recommended that the procedure (TAVR or combined WATCHMAN + TAVR) should be performed within two weeks of randomization. All patients who receive the WATCHMAN device will follow the WATCHMAN Device Implant Pharmacologic Regimen (see section 6.2.4). Patients randomized to the TAVR procedure only will be treated in accordance with standard of care with either warfarin, other anticoagulant/anti-platelet therapy, or no anticoagulation at the discretion of the treating physician. All patients will continue to receive routine post-TAVR follow-up and care. Use of the WATCHMAN device in the TAVR only arm should be avoided during the first year, unless medically necessary. All enrolled study patients shall be followed up at 45 days, 6 months, 12 months and 24 months. Follow-up beyond 1 year may be in the form of an office visit or a phone call.

Patients shall be evaluated for neurological function by NIH Stroke Scale and for modified Rankin Scale (MRS) stroke disability at baseline and each visit. In addition all patients who experience a Stroke or TIA will be evaluated by a neurologist and have brain imaging.

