6.2.3 FOLLOW-UP

Patients will have follow-up visits at 45 days following the TAVR procedure alone or post-WATCHMAN implant, and 6 months, 12 months and 24 months post -procedure. During each follow-up visit (scheduled or interim), all enrolled patients must be evaluated for adverse events using an assessment of history and physical exam. NIHSS Stroke Assessment Worksheet and MRS Stroke Assessment Worksheet should be completed at each visit.

For patients who suffer a stroke or TIA following randomization, the following assessments should be completed:

- Complete evaluation by Neurologist, AND
- Brain Imaging (CR/MRI)

Patients who received a WATCHMAN implant are required to undergo a TEE examination during the procedure and 45-days post-implant. TEE imaging must be performed in accordance with standard protocol, using color Doppler technology and possibly ECHO contrast within the LAA to confirm the absence of blood flow AROUND and/or THROUGH the WATCHMAN implant. Patients randomized to WATCHMAN who have intracardiac thrombus visualized during the procedure are contraindicated from receiving the device per labeling guidelines, but will remain in the trial as intent to treat and should be followed for all study visits.

[figure not shown]
Completion of the following assessments must be documented on the Follow-Up Case Report Form:

- The presence or lack of flow in the LAA;
- Residual atrial septal shunt;
- Thrombus on the device surface;
- Device position

Patients randomized to the TAVR alone group are to remain on anticoagulant/antiplatelet therapy at the discretion of the treating physician indefinitely if possible. If the patient is on warfarin, dosage should be adjusted such that patients maintain a therapeutic INR of 2.0 – 3.0. According to ACC/AHA/ESC Guidelines on Management of Patients with Atrial Fibrillation, INR is to be monitored per site standard of care guidelines while patients are on warfarin therapy.

All patients should continue to undergo routine post-TAVR follow-up as per accepted standards of care.

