9.4.2 ANALYSIS OF THE PRIMARY ENDPOINT

The primary endpoint is the first occurrence of all-cause mortality, stroke or major/life-threatening bleeding event within one year following randomization. Estimates of the hazard ratio and 95% confidence intervals will be based on the Cox proportional hazards model, under the assumption of proportional hazards. Comparison of cumulative hazard functions will be based on the log-rank test.

The upper bound of the confidence interval will be generated from the Cox proportional hazards model with treatment group as a factor.

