5.2 Analysis Populations

Intention-to-Treat Population (ITT):

The primary analysis will be based on the ITT population. All randomized subjects will be analyzed according to their original randomization assignment (WATCHMAN+TAVR or TAVR) regardless of treatment received. The ITT analysis will be censored at 2 years (730 days) after randomization.

Per-protocol population (PP):

The per-protocol population is defined as patients in the WATCHMAN groups who received both the WATCHMAN and the prosthetic valve. In the TAVR only group, it is defined as patients who had the prosthetic valve placed. The PP analysis will be censored at 2 years (730 days) after randomization.

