5.4.2 Durations

- Time to Event (e.g. time to primary endpoint) will be calculated as (event date/time – randomization date/time). Patients not having an event, or lost to follow-up will be censored at the minimum of the time of their last documented follow-up date, death date, or 2 years (730 days).
- Other durations of time will be calculated similarly as (date/time of interest – reference date/time +1)

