7 ANALYSES

7.1 Primary Analysis

The ITT analysis will include all positively adjudicated post-randomization primary endpoints within the ITT analysis set through 24 months (730 days) after randomization.

The study is designed to demonstrate the non-inferiority of the WATCHMAN device compared to the control group, with regards to the primary endpoint (composite of all-cause mortality, stroke (ischemic and hemorrhagic), or bleeding (major and/or life-threatening)). Non-inferiority will be assessed using the 1-sided 97.5% confidence interval around the hazard ratio (WATCHMAN-TAVR: TAVR only). Non-inferiority will be demonstrated if the 1-sided 97.5% upper confidence limit for the difference in proportions is less than 1.5. If the non-inferiority objective is met, additional analyses to assess superiority of the WATCHMAN group to the control group will be performed. The composite primary endpoint will also be summarized as events per 100 patient-years of follow-up.

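### Control-arm WATCHMAN use is discouraged for one year only, but the SAP counts primary events to day 730 and no planned analysis can show the effect of control crossover

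*Protocol*

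**What the plan says.** Protocol 3.1 is the only place that addresses use of the device in controls: "Use of the WATCHMAN device in the TAVR only arm should be avoided during the first year, unless medically necessary". Neither document states a rule for months 12 to 24. The nearest text, Protocol 6.2.3, says that TAVR-alone patients "are to remain on anticoagulant/antiplatelet therapy at the discretion of the treating physician indefinitely if possible"; it does not mention the device.

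The documents give two primary event windows. Protocol 9.4.2 counts a first death, stroke or "major/life-threatening bleeding event within one year following randomization". SAP 7.1 counts "post-randomization primary endpoints within the ITT analysis set through 24 months (730 days) after randomization", and SAP 5.2 adds: "The ITT analysis will be censored at 2 years (730 days) after randomization".

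Under SAP 5.4.2, patients without an event are "censored at the minimum of the time of their last documented follow-up date, death date, or 2 years (730 days"). Receipt of the device is not a censoring reason.

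SAP 7.4 plans one sensitivity analysis, in the per-protocol population. SAP 5.2 says of that population: "In the TAVR only group, it is defined as patients who had the prosthetic valve placed". Protocol 9.3 defines it the same way. A control who later receives WATCHMAN therefore stays in it.

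**The concern.** The rule that protects the treatment contrast and the window in which events count have different lengths. Every control met WATCHMAN labeling at entry (inclusion criterion 4), and only centers approved for commercial implantation take part, so later implantation in controls is feasible.

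A crossed-over control's later events still count as TAVR-alone events. This makes the arms more alike and moves the ITT hazard ratio towards 1. In a non-inferiority trial, that helps the claim when the device is truly worse. When the device is truly better, it costs power for the superiority test that follows. Because the per-protocol set keeps the same patients, agreement between the two planned analyses would not show that dilution was absent.

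**Working it through.** **Inputs** (Protocol 9.4.4, SAP 4): one-sided alpha 0.025, power 80%, margin 1.5, design hazard ratio 1.0, control risk 35% at one year, 10% annual dropout, 350 patients allocated 1:1, 191 events. The window is 730 days (SAP 7.1). Constant hazards and the crossover share c are my assumptions.

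**1. The plan's own figure.** Schoenfeld: 4 × (1.960 + 0.842)² / (ln 1.5)² = 190.97, rounded up to 191. This reproduces.

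**2. Share of events after the first year.** Control hazard λ = −ln 0.65 = 0.431 per year; dropout hazard η = −ln 0.90 = 0.105 per year. The probability of an observed event by time T is λ/(λ+η) × (1 − exp(−(λ+η)T)).

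- Hazard ratio 1.0: 0.333 at one year and 0.529 at two years. With 350 patients this is 117 and 185 events, so the year-2 share is 1 − 0.333/0.529 = 37%.
- Hazard ratio 1.5 (device arm hazard 1.5λ): 138 and 209 events over both arms, so the year-2 share is 1 − 138/209 = 34%.

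About 117 events in one year is far below 191. On these inputs the event-driven design depends on the second year.

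**3. Dilution when the true hazard ratio is 1.5.** Let a share c of controls who are event-free at month 12 take the device-arm hazard from then on. As year 2 begins, the control hazard is λ(1 + 0.5c), so the year-2 ratio is 1.5/(1 + 0.5c). Weighting the log ratios by event share for c = 0.30: 0.658 × ln 1.5 + 0.342 × ln(1.5/1.15) = 0.267 + 0.091 = 0.358, and exp(0.358) = 1.43. The table instead solves the large-sample Cox score equation over two years; the two agree closely.

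One-sided error = Φ((ln 1.5 − ln HR)/SE − 1.960), with SE about 0.146 at 191 events. For c = 0.30: (0.405 − 0.358)/0.146 − 1.960 = −1.64, which gives 0.051.

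| Share crossing over | All at month 12: HR, error | Spread evenly over year 2: HR, error |
|---|---|---|
| 0% | 1.50, 0.025 | 1.50, 0.025 |
| 10% | 1.48, 0.032 | 1.49, 0.028 |
| 20% | 1.45, 0.041 | 1.48, about 0.031 |
| 30% | 1.43, 0.051 | 1.47, about 0.035 |

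**4. Other true values.** At a hazard ratio of 1.0, crossover changes nothing in this model and power stays at 0.80. At 0.70 (illustrative), with all switching at month 12, superiority power at 191 events falls from 0.69 to 0.66 with 10% crossover and 0.59 with 30%.

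Events caused by the implant procedure in crossed-over controls are not modeled. They would count against the control arm.

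**The case against.** The plan chooses a treatment-policy comparison: ITT, follow-up regardless of adherence, approved devices, and a control arm treated at physician discretion. A time-limited restriction is a defensible pragmatic choice within that. This stands, and ITT is not the complaint. What remains is that the restriction and the event window do not match, and that nothing planned shows the consequence.

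The size is uncertain. The crossover rate is assumed, and switching everyone at month 12 is close to the worst case for year-2 crossover. Spreading the same shares over the year reduces the effect. If hazard is concentrated soon after the procedure, year 2 carries fewer events and the effect is smaller still. These points stand and are why a range is given.

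Four stronger readings are tempting, and the documents do not support them:

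- *Year 2 is the half of follow-up in which the contrast blurs.* It is half of the time but 34% to 37% of expected events. Crossover in year 1, which Protocol 3.1 allows when medically necessary, also dilutes the contrast, and for longer.
- *The window was lengthened and the rule forgotten.* The first-year rule agrees with Protocol 9.4.2, but neither document shows that history.
- *The restriction should run for two years.* That is a clinical rule for the sponsor. The documents show only that the sections disagree.
- *Crossovers will go unrecorded.* The protocol and SAP text does not ask for their reporting, but the case report form is not among the documents and the flow diagram is not legible in the available text. Existing capture cannot be judged.

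**Conclusion.** The mismatch holds on the text. Device use in controls is discouraged for one year, consistently with Protocol 9.4.2, while the SAP's primary analysis runs to day 730 with no handling of crossover, and its per-protocol set keeps crossed-over controls.

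The statistical consequence is conditional. It needs crossover to occur and the true hazard ratio to differ from 1.0. With 10% to 30% crossover in year 2 and a true hazard ratio at the margin, the error is about 0.028 to 0.051 against a nominal 0.025. That is modest at 10%, and about double nominal only if 30% switch at month 12. It rests on constant hazards and on switched controls taking the device-arm hazard. It does not show that the trial's conclusion would be wrong. It does show that, as planned, a reader could not judge whether dilution had contributed to it. The sponsor should correct this.

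**What to change.** 1. Reconcile Protocol 3.1 and 9.4.2 with SAP 5.2 and 7.1, so that the crossover rule and the primary event window refer to a consistent period. The sponsor decides the clinical rule. State whether the first year in Protocol 3.1 runs from randomization, as the event window does, or from the procedure.
2. Keep ITT as the primary analysis.
3. Record the date and reason of every WATCHMAN implant in the control arm, if this is not already captured, and report the number by follow-up year beside the primary result.
4. Add to SAP 7.4 a pre-specified sensitivity analysis of the primary endpoint that handles crossover, for example by censoring controls at implant.

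The cost is a wording change, a small amount of extra data and one more analysis, with no extra visits. Patients who cross over may differ in risk from those who do not, so censoring at implant may be informative. That analysis is supportive only.

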9.4.4 SAMPLE SIZE

The WATCH-TAVR is a randomized, prospective multi-center event-driven non-inferiority study to determine the safety and efficacy of the WATCHMAN device in patients with non-valvular AF undergoing TAVR for aortic stenosis. The control group consists of patients undergoing TAVR who are on standard medical practice, with oral anticoagulation at the discretion of the treating physician. The treatment group will have the WATCHMAN implantation procedure performed simultaneously with TAVR. The primary endpoint is a composite of all-cause mortality, stroke, life-threatening or major bleeding. The objective of the study is to demonstrate non-inferiority of the TAVR plus WATCHMAN device compared to the TAVR only group.

Data from the PARTNER¹ trial, along with the SOURCE-XT¹⁰ and FRANCE-2¹¹ registries show all-cause mortality rates in TAVR patients with AF vary from 19-30%, stroke rates from 6-10% and major/life-threatening bleeding from 17-22%. The PROTECT-AF trial for the WATCHMAN device in non-valvular atrial fibrillation patients reported a risk reduction of nearly 40% for the primary composite endpoint of stroke, systemic embolization or cardiovascular or unexplained death (RR 0.61, 95%CrI 0.42-1.07)⁴.

The following assumptions were used to determine the sample size needed to assess the non-inferiority hypothesis for the composite primary endpoint of all-cause mortality, stroke or major or life-threatening bleeding:

- One-sided $\alpha = 0.025$
- Primary event rate in the control population (TAVR only) of 35% at one year
- Non-inferiority margin of 1.5
- Underlying hazard ratio of active to control is 1.0
- Power at least 80%
- Lost to follow-up rate 10%

Assuming level of significance (α) to be 0.05 (or $\alpha = 0.025$ one-sided) and aiming for a study power ($1 - \beta$) of 80%, we estimate 191 primary events will be needed to rule out an upper limit of the one-sided 97.5% confidence interval of 1.5. Assuming an enrollment duration of 18 months, follow-up period of 24 months, and 10% drop out rate per annum, the minimum total sample size required is 350 (175 per group).

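### The only scheduled contact after month 12 may be a phone call, which cannot deliver the examination the protocol requires, and it may fall before day 730; the main cost is events and power

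*Protocol*

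**What the plan says.** Protocol 3.1 schedules contacts at 45 days and at 6, 12 and 24 months, and adds: "Follow-up beyond 1 year may be in the form of an office visit or a phone call". A footnote to the schedule tables in Protocol 6.2.1 and SAP 3.3 repeats this for Visit 5.

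Protocol 6.2.3 says that at each follow-up visit "all enrolled patients must be evaluated for adverse events using an assessment of history and physical exam", and that NIHSS and mRS worksheets are to be completed each time. The tables in both documents mark NIHSS and mRS at month 24 in both arms. They disagree on vital signs at that visit: blank in the protocol, marked in the SAP.

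The visit is timed at 24 months ± 1 month from the procedure. SAP 7.1 counts adjudicated "post-randomization primary endpoints within the ITT analysis set through 24 months (730 days) after randomization", and SAP 5.4.2 censors patients without an event at their last documented follow-up, capped at 730 days. Protocol 9.4.2 instead limits the primary endpoint to one year.

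**The concern.** A physical exam cannot be done by phone, and neither document says how NIHSS or mRS would be obtained that way. Nothing is scheduled between months 12 and 24. For a patient who is phoned, a non-fatal stroke or a VARC2 major bleed in that year may come to light only if the patient remembers and reports it. The protocol's background section says: "The TAVR population is at increased long-term bleeding risk, with cognitive impairment, high risk of falls". That describes TAVR patients in general rather than those enrolled, but it makes recall a weak sole source. Neurologist review and imaging start only once a stroke or TIA is recognised, and adjudication cannot recover an event that was never submitted.

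The timing adds a second, smaller loss. A last contact that meets the visit window but precedes day 730 ends that patient's observation early. Because the analysis stops at day 730, longer follow-up cannot make up for events lost either way.

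**Working it through.** **Inputs from Protocol 9.4.4 and SAP 4.** One-sided alpha 0.025, power 80%, margin 1.5, true HR 1.0, 35% control event rate at one year, 10% annual dropout, 350 patients, 191 events.

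**Assumptions not in the documents.** Constant hazard; half of first events fatal; 20–60% of year-2 non-fatal events missed.

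**1. The plan's event count.** 4 × (1.960 + 0.842)² / (ln 1.5)² = 190.97, so 191 is reproduced.

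**2. Events by year.** The event hazard is λ = −ln 0.65 = 0.431 per year and the dropout hazard is η = −ln 0.90 = 0.105. P(event by t) = λ/(λ+η) × [1 − exp(−(λ+η)t)].
- P(1) = 0.333, or 117 events in 350 patients.
- P(2) = 0.529, or 185 events.
- Year 2: 185 − 117 = 68, and 68/185 = 37%.

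If the 10% dropout covers the whole two years, 193 events are expected and the share is 38%. With no dropout it is 80 of 202 (39%). If the year-2 risk is assumed to be 15–30% instead of 35%, the share is 20–33%.

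**3. Equal missing in both arms, true HR 1.0.** At one year 350 × 0.65 × 0.90 = 204.75 patients are still at risk. If a fraction m of non-fatal events is missed, the recorded year-2 hazard is λ(1 − 0.5m). A patient whose event is missed stays at risk and may still have a later event recorded. Power = Φ(ln 1.5 × √D / 2 − 1.960), where D is the total number of recorded events.

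| Missed (m) | Year-2 events | Total D | Power |
|---|---|---|---|
| 0 | 68.3 | 185.0 | 78.7% |
| 20% | 62.7 | 179.4 | 77.5% |
| 40% | 56.8 | 173.5 | 76.1% |
| 60% | 50.7 | 167.4 | 74.6% |

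**4. Effect on the hazard ratio.** This uses a two-arm constant-hazard model, solved for the Cox estimate.
- Equal missing, same HR for fatal and non-fatal events: 1.0 stays 1.000 and 1.5 stays 1.500.
- Equal missing, harm only in non-fatal events (HR 2.0 non-fatal, 1.0 death): the composite HR of 1.50 becomes 1.48, 1.46 and 1.44 at 20, 40 and 60% missed. The chance of a false non-inferiority finding rises from 2.5% to 3.1, 3.8 and 4.7%.
- Unequal missing at a true HR of 1.5: 1.44 if 40% are missed on device and 20% on control; 1.56 if reversed.

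**5. Early final contact.** Protocol 3.1 recommends the procedure within two weeks of randomization. With the procedure on day 0 to 14 and the visit 30 days early, the last contact falls at day 700 (730 − 30) to day 714 (14 + 730 − 30). Expected events after that point are 350 × [P(2) − P(700/365)] = 4.3 and 350 × [P(2) − P(714/365)] = 2.3. This is about 2 to 4 events if every final contact were that early.

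**The case against.** The strongest reply is that event capture does not depend on the scheduled contact. Protocol 7.2 makes death, stroke, TIA and bleeding reportable whatever their cause, and asks for deaths and serious injuries within 24 hours of the site learning of them. Protocol 6.2.3 foresees interim visits, continued routine post-TAVR care, and INR monitoring for patients on warfarin. Protocol 4.4 seeks vital status on everyone. The monitoring plan and eCRF content are not among the documents and may contain record checks. This stands in large part: year 2 does not rest on one contact, and deaths are well protected. It does not cover a non-fatal event that the site never learns of, and nothing in the two documents requires a search for one.

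A reader might also infer that missed events pull the arms together and so favour non-inferiority. The documents do not support that. Equal missing leaves a common hazard ratio unchanged, and the lost power works against a non-inferiority claim. Dilution needs an effect concentrated in stroke and bleeding. That is conceivable given the trial's aim, but it is an added assumption and the shift is small.

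A shift of 4–7% from 3 to 7 lost events is a similar over-reading. Of 68 year-2 events about 34 are non-fatal, or 17 per arm. Placing all the losses in one arm (about 3.4 to 6.8 of some 92 events) means 20–40% missed there and none in the other. Nothing in the documents says contact mode will differ by arm, and unequal capture could bias either way.

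Finally, censoring before day 730 is handled by SAP 5.4.2. It costs person-time and does not in itself bias the comparison.

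**Conclusion.** The point holds as an internal contradiction and an avoidable loss of information. The documents conflict on what the 24-month contact contains, give no phone method, and let the last contact precede the end of the endpoint window.

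The size is modest: about 1 to 4 percentage points of power at 20–60% missed, plus up to about 2 to 4 events from early final contacts, fewer if the vital-status check recovers deaths. This matters because there is little slack. On 10% annual dropout the plan expects 185 events against 191 needed; on 10% over two years it expects 193.

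The figures rest on constant hazard, half of events being fatal, and assumed missing fractions. They apply under the SAP's 730-day window. Under the one-year wording of Protocol 9.4.2, year 2 would contribute no primary events and about 117 would be expected, far below 191, so those two passages must be reconciled as well.

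**What to change.** - Reconcile Protocol 3.1, 6.2.1 and 6.2.3 with SAP 3.3 on what the 24-month contact contains, including how NIHSS and mRS are handled by phone and whether vital signs are taken. Reconcile Protocol 9.4.2 with SAP 7.1 on the endpoint window.
- Where the contact is by phone, use one scripted stroke and bleeding questionnaire, put to the patient and, where available, an informant. Add a request for records of hospital and emergency contacts since month 12. Apply both identically in the two arms.
- Require the final event-ascertainment contact on or after day 730 from randomization.
- Record the mode of contact and report it by arm.

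The cost is protocol and CRF wording, one form, and a little more site work at month 24 for the record requests. An in-person visit need not be required: it would burden a frail population and could cost retention, and the scripted contact with record requests addresses the gap without it.
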